Pre-Screening for Cohort 2: Through a voice call or in-person meeting with study staff, or via the HIPAA-compliant online portal process described above for Cohort 1, interested individuals will be provided with a thorough description of the requirements of the study. Interested SZ volunteers will be asked screening questions about demographics, likely diagnosis, MRI eligibility and cognitive ability. Volunteers will also complete items from a neuropsychological vocabulary test to estimate crystalized IQ. Research staff will then inquire about the participant's transportation needs and offer assistance as needed to attend any in-person study appointments. If the SZ volunteer fulfills inclusion and exclusion criteria they will be invited to participate and scheduled for a pretest assessment.

Screening/Baseline Visit for Cohorts 1 and 2:

After the initial consent form has been signed, all participants will undergo the following assessments:

- The MINI – to rule out current Serious and Persistent Mental Illness (SPMI) and addictive disorders for Cohort 1, and to confirm diagnosis and rule out addictive disorders for Cohort 2.

Prior to randomization, eligible participants in both cohorts will be characterized at baseline and tracked across the study (see schedule of events tables) using cognitive tasks, clinical assessments, and neuroimaging. These include the following*:

- MATRICS Consensus Cognitive Battery Subtests (including Symbol-Coding, Category Fluency, Trailing Making Test, Spatial Span; Letter-Number Span; Hopkins Verbal Learning Test) (Cohort 1 and 2)
- UCSD-Performance Based Skills Assessment – Brief (UPSA-B) (Cohort 2 only)
- Brief Psychiatric Rating Scale (BPRS) (Cohort 2 only)
- Brief Negative Symptom Scale (BNSS) (Cohort 2 only)

* In the case that study assessment visits are conducted remotely, some of these measures (e.g. Spatial Span) will not be collected.

PROTOCOL TITLE: Increased thalamocortical connectivity in tDCS-potentiated generalization of cognitive training

VERSION DATE: January 26, 2023

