
Analyses to test SA2, that generalization and durability are driven by right tDCS more than left tDCS or sham (H2.1), longer treatment length (H2.2) and higher modeled dosage (H2.3) will be conducted both between and within groups (for both Studies 1 and 2). The first step will establish the existence of between-group training effects using repeated-measures ANOVA’s on the key performance outcome variables (d' scores for the word and picture N-backs, d'-context for the DPX, and the composite score for MCCB). We will also evaluate differences in self-rated engagement and experimenter-rated Work Behavior Inventory (Bryson et al., 1997), sleep patterns, age, baseline IQ, and these will be used as covariates of non-interest as appropriate.

PROTOCOL TITLE: Increased thalamocortical connectivity in tDCS-potentiated generalization of cognitive

training

VERSION DATE: January 26, 2023

To examine SA3, the relationship between thalamocortical FC change and generalization and durability, we will examine the nonparametric relationships between changes in thalamocortical connectivity and improvements on the trained task (word N-back d'), proximal transfer (picture N-back d'), and more distal generalization (DPX d', MCCB composite score) and durability (H3.1 and H3.2 respectively). If analysis of covariates suggest that there are important sources of within-group variance in learning (e.g. age, baseline IQ, etc.), then hierarchical regressions will be used on Fisher's transformed z-scores of thalamocortical connectivity. In addition, to determine whether thalamocortical FC changes predict stability in learning and generalization, task performance at 24 weeks will also be subjected to hierarchical regressions. The regression model will enter covariates on step 1, and thalamocortical connectivity on step 2. The statistician will be blind to condition until analyses are completed.

In all cases, these relationships will be tested separately for Cohort 1 and Cohort 2, as changes associated with improvement are likely to be different for groups with different mean levels of ability. Follow-up analyses will determine the extent to which these observed differences suggest actual differences between these populations. However, the current study is not designed to directly compare the populations.

15.2 Power Analysis:

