75 completers in cohort 1 and cohort 2 will provide power of .80 to detect effects as small as $\eta^2=.03$ for key confirmatory analyses (tested at $\alpha = .05$) and $\eta^2=.05$ for other analyses (tested at $\alpha=.005$), with nearly as strong power for the analysis of the 24 week follow-up. The more conservative approach of intent-to-treat analysis ($n=90$) will also be conducted for Cohort 2, for which the study will be sensitive to $\eta^2=.027$ (tested at $\alpha = .05$) and $\eta^2=.042$ (tested at $\alpha = .005$). These effect sizes are much smaller than the group x time effect for generalization as measured by the MCCB in our pilot tDCS data ($\eta^2=.08$), suggesting the proposed study is well-powered. While power analyses for neuroimaging studies are challenging due to the interactions of voxelwise-thresholds, brain-wise error correction and spatial smoothness, the proposed studies will be well-powered to detect group x time voxel differences as small as $\eta^2=0.07$ (tested at $\alpha = .001$), and in any case the samples are twice the size of our previous, successfully replicated, neuroimaging studies of brain change following cognitive remediation. Within-group responder analyses conducted for completers ($n=25$ per cell) will have power of .80 to detect correlations $r \geq .34$, a lower magnitude than we already observed ($r=.55$).

15.3 Statistical Analysis:

See section 16.1

15.4 Data Integrity:

The investigator is responsible for ensuring the accuracy, completeness, legibility, and timeliness of the data reported. To enhance scientific rigor, avoid bias and enhance reproducibility, our triple-blind randomized design will use a stratified permuted block randomization procedure (Matts & Lachin, 1988) to roughly equate age and baseline WM performance across groups with a block size of 6. Neither participants nor experimenters will know group assignment. TDCS software programming will allow staff to randomly select one of the three hemisphere conditions (right, left, sham) corresponding to eight letters (six to be distributed evenly among three conditions for HCs, two to be distributed evenly among two conditions for SZs) encoded to preserve the blind. Randomization will be facilitated and the blinding code will be maintained by the study statistician.

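### SA2 compares arms by repeated-measures ANOVA with no baseline-adjusted model; randomisation is stratified on age and baseline working memory, but age is an optional covariate and baseline working memory is not named

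*Combined protocol and SAP*

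**What the plan says.** Section 15.1, on SA2: "The first step will establish the existence of between-group training effects using repeated-measures" ANOVA. The outcomes are d' on the word and picture N-backs, d'-context on the DPX, and the MCCB composite. The next sentence says that differences will be evaluated in self-rated engagement, the Work Behavior Inventory, "sleep patterns, age, baseline IQ", and that "these will be used as covariates of non-interest as appropriate". Nothing says when a covariate is appropriate.

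No SA2 model takes the baseline score of the outcome as a covariate. The regressions in 15.1 that enter covariates first belong to SA3, which relates connectivity change to performance and does not compare arms. Section 15.3 refers the reader to section 16.1, which is about data security.

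Section 15.4 describes stratified permuted blocks "to roughly equate age and baseline WM performance across groups with a block size of 6". It does not define the WM measure.

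On availability of the data, section 5.2 says: "Prior to randomization, eligible participants in both cohorts will be characterized at baseline and tracked across the study".

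On size, section 15.2 says: "75 completers in cohort 1 and cohort 2 will provide power of .80" at alpha .05 for eta-squared .03. It compares that with a pilot group x time effect of .08 on the MCCB.

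**The concern.** There are three linked points.

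- **Precision.** With baseline as one of the waves, a group x time test compares change scores. Under randomisation, using the baseline score as a covariate estimates the same arm effect with a variance that is never larger, apart from the degree of freedom spent.
- **Match to the randomisation.** Stratifying on a prognostic factor and then leaving it out of the model makes standard errors too large. Baseline WM is likely to be prognostic here, because two of the four outcomes are N-back scores.
- **Open covariate rule.** A set chosen after looking at differences lets the data pick the model. The candidates also include engagement and the Work Behavior Inventory, which section 5.2 has rated at training sessions, after randomisation. Treatment may affect them, so adjusting for them can bias the arm comparison.

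What is at stake is mainly efficiency, in a trial whose section 4.1 already expects Cohort 2 to be smaller than planned.

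**Working it through.** **1. Can the plan's own figures supply rho?** Take f² = eta²/(1-eta²), N = 75, eta² = .03, alpha .05.

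- Plain between-group ANOVA, lambda = f²N: power is .25 with three arms and .32 with two. The stated .80 is not reproduced.
- Repeated-measures interaction, lambda = f²Nm/(1-rho) with m waves. For three arms, two waves and rho .5, power is .77. The smallest detectable eta² is .0324 (alpha .05) and .0532 (alpha .005) at N = 75, and .0270 and .0442 at N = 90. Section 15.2 states .03, .05, .027 and .042.
- Three arms, two waves and rho .52 puts all four stated figures at power .78 to .82. So does two arms, three waves and rho about .27.

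The figures fit several layouts, each with its own rho, so rho must be assumed. I use .5 to .8.

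**2. Variance ratio, baseline and one later visit.** In units of the outcome variance, per participant:

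- change score: 2(1-rho)
- adjusted for baseline: 1-rho²
- ratio: (1-rho²)/[2(1-rho)] = (1+rho)/2

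**3. Effect on power.** A two-sided .05 test with power .80 has a standardised effect of 1.960 + 0.842 = 2.802. After adjustment, power is Phi(2.802/√ratio - 1.960). For rho .5 this is 2.802/√.75 = 3.235, less 1.960 = 1.275, and Phi is .90.

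| Assumed rho | Variance ratio | Variance saved | Power, from .80 | Simulated | Completers equivalent to 75, 75(1+rho)/2 |
|---|---|---|---|---|---|
| .5 | .75 | 25% | .90 | .89 | 56 |
| .6 | .80 | 20% | .88 | .87 | 60 |
| .7 | .85 | 15% | .86 | .86 | 64 |
| .8 | .90 | 10% | .84 | .83 | 68 |

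The simulation used two arms of 37 and 38, 6,000 runs per row, and an unadjusted power of .79 to .80.

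**4. More than one later visit.** The schedules in 5.2 give the MCCB at four visits and scanning at three. If two later visits are averaged and all correlations are equal, the change form has variance (1+rho)/2 + 1 - 2rho and the adjusted form (1+rho)/2 - rho². At rho .5 that is .50/.75 = .67. At rho .7 the ratio is .80, and at .8 it is .87. The direction is the same but the size changes.

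**5. Stratification factors against covariates.**

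| Variable | Stratifies (15.4) | SA2 covariate (15.1) | Measured |
|---|---|---|---|
| Age | yes | optional | before randomisation |
| Baseline WM | yes | not named | before randomisation |
| Baseline IQ | no | optional | before randomisation |
| Engagement, Work Behavior Inventory | no | optional | during training |

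Baseline IQ is estimated from a vocabulary test and does not stand in for baseline WM.

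**The case against.** The planned analysis is not wrong. Repeated-measures ANOVA with baseline as a wave uses the baseline and is valid under randomisation, and omitting stratification factors errs towards caution. Both statements stand, so this is a gain in efficiency and not the repair of a bias.

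The size is also uncertain, and several stronger readings do not hold.

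- *Section 15.2 implies rho .5.* A reader might infer this, but other layouts fit as well with a different rho.
- *For the pilot eta² of .08, power would rise from .60 to .74.* This takes lambda = (.08/.92) x 75 = 6.52 from a scale on which eta² .03 has power only .25, and rho .5 from another. On that other scale lambda is 6.52 x 2/.5 = 26.1 and power is already .996.
- *Every SA2 comparison has 25 completers per cell.* That fits the three arms of Cohort 1. Cohort 2 has two arms, so 75 completers would be about 37 or 38 each.
- *Age and baseline WM add a further gain.* The WM measure is undefined. If it is an N-back score it may repeat the baseline of an N-back outcome.
- *Covariates will be chosen by imbalance between arms.* The text does not say between which groups differences are evaluated. The SA3 paragraph speaks instead of within-group variance in learning, and the statistician is to stay blind until analyses are complete. The rule is open, and selection by imbalance is only one reading.
- *The test is the group main effect averaged over baseline and follow-up.* The loss would then be far larger, but 15.2 speaks of group x time.

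**Conclusion.** The point holds as a free improvement. SA2 specifies a less precise method than the data allow, and its covariate rule does not match the randomisation: age is optional and baseline WM is absent.

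For group x time on baseline and one later visit, baseline adjustment saves 25% to 10% of the variance for rho .5 to .8, and lifts a power of .80 to about .90 to .84. This rests on an assumed rho, equal variances at the two visits and a single later visit. The direction does not depend on rho as long as it is below 1. No size is claimed for adding the stratification factors.

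The rule that leaves engagement and the Work Behavior Inventory open as covariates should go in the same edit, because adjusting for them could affect validity as well as precision.

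**What to change.** In 15.1, separately for each cohort, replace the SA2 ANOVA with a model of post-baseline scores on arm, visit, arm x visit and the baseline score of that outcome.

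- Always include age and baseline WM performance. Define the WM measure used to stratify, and drop that term where it is the same measure as the outcome's baseline.
- Fix the covariate set in advance. Remove the step that looks at differences before deciding.
- Do not adjust the arm comparison for engagement, the Work Behavior Inventory, session-reported sleep or anything else measured after randomisation. Such variables can be described by arm.
- State how missing baselines are handled. Under section 5.7, remote participants may have no scanner tasks and no Spatial Span, so some outcomes will lack a baseline or have a reduced MCCB composite.

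The cost is wording and a few degrees of freedom. The baseline measures are already scheduled before randomisation. The edit should be made before the blind is broken.

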WM focused training occurs on a computer and consists of a variety of exercises selected to i) place demands on the executive and storage functions of working memory ii) adapt to challenge the participant's current ability level, iii) provide ongoing feedback, and iv) present novel stimuli across verbal, visual and spatial modalities. Training tasks are developed in-house. Tasks for each subject are delivered from our AHC-IS server (cnc2.med.umn.edu). Responses of subjects and session audio and video are saved on our AHC-IS server for analysis of training performance and engagement. The aim of using multiple tasks that require WM functions is to engage thalamocortical connectivity in a number of different ways to promote generalization. The intervention will be provided by the experimenter in small groups of four or fewer participants (4:1 ratio of participants to experimenters) working under the supervision of Drs. [name] and [name], in consultation with Co-I [name], following a protocol developed by Drs. [name] and [name]. In this scheme, experimenters will monitor each participant's training and customize the intervention to balance challenge and engagement. In addition, each week participants will perform 4-minute versions of a word and a spatial 3-back task that will remain the same across all weeks (but differ from the assessment versions) to allow us to track training improvements using a constant difficulty level.

Participant effort will be rated by experimenters at each session using the Work Behavior Inventory (Bryson, Bell, Lysaker, & Zito, 1997). Just before the end of each training session, subjects will complete a brief questionnaire that also asks about their perceived engagement in the training that day, as well as their mood, previous night's sleep, discomfort, and their perceived experimental condition. Finally, at the end of each session, the participant will select the final task from an array of fun games, which we have found promotes agency and improves attendance.

Genetic sampling procedures (Baseline and Week 12):

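### SA2: Cohort 1, the only cohort with a right-tDCS arm, has no stated all-randomised analysis, and covariates recorded after randomisation are not kept out of the between-group test

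*Combined protocol and SAP*

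**What the plan says.** Section 3.1 defines H2.1 as greater generalization and durability with right tDCS than with left tDCS or sham. Sections 4.1 and 5.1 give Cohort 1 three arms (right, left, sham; 90 randomised) and Cohort 2 two arms (left, sham).

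Section 15.1 says that the SA2 analyses "will be conducted both between and within groups". It begins with the between-group comparison: "The first step will establish the existence of between-group training effects using repeated-measures" ANOVA on the N-back, DPX and MCCB outcomes. It names no analysis population. The next sentence reads "We will also evaluate differences in self-rated engagement and experimenter-rated Work Behavior Inventory" and continues, after the citation, "sleep patterns, age, baseline IQ, and these will be used as covariates of non-interest as appropriate".

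Section 5.2 gives the timing of those variables. On effort: "Participant effort will be rated by experimenters at each session using the Work Behavior Inventory". On engagement, just before each session ends, "subjects will complete a brief questionnaire that also asks about their perceived engagement in the training that day, as well as their mood". The same questionnaire asks about the previous night's sleep.

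Section 15.2 states that "75 completers in cohort 1 and cohort 2 will provide power of .80 to detect effects as small as" an eta-squared of .03 (alpha .05), or .05 (alpha .005). It then adds an intent-to-treat analysis (n=90) for Cohort 2 alone. Under section 5.2, fewer than 24 sessions does not count as complete. Sections 12.2 and 12.3 say that data collected before withdrawal or termination will be used. Section 15.3 only refers to 16.1, which concerns data security.

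**The concern.** There are two gaps, and both bear on the arm contrast.

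**Population.** Completing 24 sessions is an event after randomisation. A comparison restricted to completers is protected by randomisation only if completion is unrelated to arm, or unrelated to outcome. The plan guards against this with intent-to-treat in Cohort 2 but does not say so for Cohort 1, where H2.1 has to be tested. The clauses in 12.2 and 12.3 keep partial data but define no all-randomised set, and 12.2 leaves final assessments after withdrawal to case-by-case decision. The named method, repeated-measures ANOVA, in its standard form drops anyone with a missed visit, which sits badly with those clauses.

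**Covariates.** Age and baseline IQ are fixed before treatment. Engagement, the Work Behavior Inventory and session sleep are not. If stimulation changes engagement, adjusting the arm contrast for engagement takes out part of the effect being estimated. The text does not say which variables may enter which model.

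**Working it through.** **1. The plan's own sensitivity figure.** For a group-by-time interaction, f² = η²/(1−η²), λ = f²·N·m/(1−ρ), with df (k−1)(m−1) and (N−k)(m−1). The plan gives neither the number of time points m nor the correlation ρ; I assume m=2 and ρ=.5, with k=3 groups. At N=90 and η²=.027, λ = (.027/.973)×90×2/.5 = 9.99 and power at alpha .05 is .801, so the stated .027 reproduces. The other detectable values come close:

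| N, alpha | Plan | Repeated-measures convention | One-way ANOVA on change |
|---|---|---|---|
| 75, .05 | .03 | .032 | .118 |
| 75, .005 | .05 | .053 | .184 |
| 90, .05 | .027 | .027 | .100 |
| 90, .005 | .042 | .044 | .156 |

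The .027 is stated for Cohort 2, but it reproduces with three groups, which is Cohort 1's layout. With complete outcome data, moving Cohort 1 from 75 completers to 90 randomised would improve the detectable η² from about .032 to .027. The gain is smaller with incomplete follow-up.

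**2. Planned loss.** 90 − 75 = 15, and 15/90 = 16.7%, or about 5 of 30 per arm.

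**3. Completer bias (splits and correlations assumed).** Suppose a latent tendency to complete has correlation r with outcome, there is no true effect, and a fraction p of an arm fails to complete. The completers' mean in that arm then shifts by r·φ(z_p)/(1−p), in SD units. The bias is the difference between arms.
- 25% v 8.3%: r×(0.424 − 0.167) = 0.08 at r=.3 and 0.13 at r=.5.
- 20% v 13.3%: r×(0.350 − 0.248) = 0.03 and 0.05.
- 16.7% in both arms: 0.

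Simulation with 30 per arm gives the same values. Type I error runs from about 5% (equal split) to about 7.5% (25% v 8.3%, r=.5).

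**4. Adjusting for engagement (paths assumed).** Let tDCS shift engagement by a SD, and let engagement affect outcome with coefficient b. Adjustment removes a×b:
- 0.2×0.3 = 0.06 SD
- 0.3×0.4 = 0.12 SD
- 0.5×0.5 = 0.25 SD
- a=0: nothing

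This applies if the covariate enters an endpoint ANCOVA or a covariate-by-time term. As a main effect only, it leaves the group-by-time test unchanged.

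**5. Power consequence.** Section 15.2 cites a pilot group-by-time η² of .08, so f = √(.08/.92) = 0.295. Under the repeated-measures convention λ = 4f²N. For two equal arms compared on change, λ = N·d²/4. Hence d = 4f = 1.18 SD of change. With 25 completers per arm, unadjusted power is 98.3%. Adjusted power for the three non-zero path pairs is 98.0%, 97.6% and 94.6%.

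**6. What removing the session covariates gives up.** With a=0 and b=0.4, adjustment improves precision: power is 99.3% adjusted against 98.3% unadjusted at 1.18 SD, and 60.0% against 53.3% at a smaller effect of 0.59 SD.

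**The case against.** The strongest reply is that nothing in the plan excludes non-completers from Cohort 1. The 75 of 90 may be only an attrition allowance in a power calculation, and 12.2 and 12.3, neither limited by cohort, say partial data will be used. That stands. A reader might infer that Cohort 1 will be analysed on completers only, but the documents do not say so. What remains is that no all-randomised analysis is stated there, while one is stated for the other cohort.

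On covariates, SA2 is analysed within groups as well as between them, so within-group use of engagement and effort is a fair reading. A reader might infer that the arm contrast will certainly be adjusted for them, or that stimulation changes engagement. The text establishes neither. The omission is the missing restriction.

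One might also suspect that covariates could be chosen to favour an arm. Section 15.1 says "The statistician will be blind to condition until analyses are completed", which limits this, although 15.4 has the study statistician keep the code. Blinding does not prevent over-adjustment or selection of completers.

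A much larger power loss (53% to 26%) follows if the pilot η² of .08 is read as a change-score effect of 0.59 SD. The documents do not support making that the headline. That convention gives detectable effects of .118 and .184 where the plan states .03 and .05. The 53% also presumes 25 v 25, whereas the form of the H2.1 contrast is not stated; right against left and sham pooled (25 v 50) would give 66%.

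Finally, completers are a defensible set for the treatment-length and modeled-dosage hypotheses. That is accepted below.

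**Conclusion.** The point holds as two wording gaps, and they are worth closing because they affect the contrast that tests H2.1. It is certain from the text that intent-to-treat is stated only for the cohort without a right-tDCS arm, and that variables recorded during treatment are not barred from the between-group model. Bias is possible, not shown. Completer bias requires completion to differ by arm and to relate to outcome. Over-adjustment requires tDCS to alter engagement and the covariate to enter in a form that touches the arm contrast.

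Under the assumptions above, the sizes are 0 to 0.13 SD for completer bias and 0 to 0.25 SD of effect removed by adjustment. Power falls from 98% to 95% at most under the convention that comes close to the plan's own figures. The dropout splits, correlations and paths are all assumed. Cohort 2 is less exposed on population because intent-to-treat is already planned there, but the covariate gap applies to both cohorts.

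**What to change.** - **Population.** Extend the all-randomised analysis already planned for Cohort 2 to Cohort 1, and make it the main between-group SA2 test there. Analyse by assigned arm on all available visits, for example with an arm-by-visit mixed model, which also fits 12.2 and 12.3. Keep completers as a sensitivity analysis and for the treatment-length and modeled-dosage questions.
- **Covariates.** Limit between-group adjustment to prespecified baseline variables: age and baseline working memory (the factors that randomisation balances under 15.4) and baseline IQ. Report engagement, the Work Behavior Inventory and session sleep by arm, and use them only in within-group or exploratory analyses.

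The cost is SAP wording and a different model call; no new data are needed. There are two downsides. The all-randomised estimate may be diluted relative to completers, which the retained completer analysis would show. If tDCS does not alter engagement, some precision is given up, for example 60% to 53% power at 0.59 SD with a 0.4 engagement-outcome path. The mixed model also relies on missing data being explained by what was observed; a delta-adjusted sensitivity analysis is optional.

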2.0 Background

2.1 Significance of Research Question/Purpose:

The premise of the proposed work is that tDCS concurrent with multi-session working memory (WM) focused cognitive training facilitates durable increases in thalamo-prefrontal cortical (hereafter thalamocortical) functional connectivity (FC), and that this in turn enhances generalization to novel tasks. Due to its putative effects on plasticity and brain circuitry, tDCS is emerging as an important tool that may eventually be part of the next generation of psychiatric and neurological interventions (Andre Russowsky Brunoni et al., 2012). However, given the simple and non-focal nature of this intervention, significant questions about the mechanisms of action relevant to cognition remain unanswered (Bikson, Name, & Rahman, 2013; Flavio Fröhlich & Schmidt, 2013). Given that a 2 mA current from tDCS induces a low electrical field that causes subthreshold membrane polarization and does not carry any biological information, how can it potentiate improved performance on complex cognitive tasks or reduce diverse symptoms (Andre R. Brunoni et al., 2014; Kekic, Boysen, Campbell, & Schmidt, 2016; Trumbo et al., 2016)? Most critically for the current application, can understanding the neuroanatomy of tDCS-induced functional changes aid in optimizing tDCS for clinical applications?

2.2 Preliminary Data:

We have demonstrated that WM focused training increases left middle frontal gyrus (MFG) activity. This was first reported in a sample of n=9 experiment subjects with schizophrenia (compared to n=9 in the active control condition (Haut, [name], & [name], 2010)), and was recently replicated in n=15 patients (compared to n=12 in the active control (Ramsay, [name], Marggraf, & [name], 2017)). We observed significantly greater increases in connectivity following WM training compared to the active control treatment in both right MFG ($\eta^2=.35$) and ACC ($\eta^2=.29$). These effects were driven by increased thalamocortical connectivity in the experimental group. Importantly, those who showed the greatest increases in thalamocortical connectivity also had the most general transfer on the MCCB in the experimental group ($r=.55$, $p=.043$, but not in controls).

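### SA3 supplementary week-24 regression: the same measure's baseline score is not named on step 1, so the model may describe week-24 level rather than gain kept

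*Combined protocol and SAP*

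**What the plan says.** The SA3 part of section 15.1 has two layers. The main test relates change in thalamocortical connectivity to improvement on the N-back, DPX and MCCB measures, so it already works with change. A further regression is then added "to determine whether thalamocortical FC changes predict stability in learning and generalization". For that purpose, "task performance at 24 weeks will also be subjected to hierarchical regressions". Its terms are given in one sentence: "The regression model will enter covariates on step 1, and thalamocortical connectivity on step 2".

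The covariates are described only as "important sources of within-group variance in learning (e.g. age, baseline IQ, etc".). The SA2 list in the same section adds engagement, the Work Behavior Inventory and sleep. Neither list names the baseline score of the measure being analysed. Section 15.3 refers the reader to 16.1, which is Data Security and adds no analysis detail. Baseline working memory does appear in section 15.4, but as a stratification factor for randomization, "to roughly equate age and baseline WM performance across groups".

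**The concern.** Stability of learning needs a reference point. In the added regression no reference is named: no baseline score, no week-12 score, and no change score as the outcome. With only age and baseline IQ on step 1, the step-2 coefficient says whether people with larger FC change score higher at week 24. Those people may simply have scored higher from the start.

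Randomization does not settle this. Stratification balances arms, whereas this regression is at person level within a cohort or arm, and FC change is not randomized. A correlation between FC change and baseline score therefore cannot be excluded by design.

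Two things are at stake. If FC change and baseline are unrelated, baseline variance left in the residual costs power, and a null result becomes hard to read. If they are related, a positive result could be reported as durable learning when no gain was kept. Durability is H3.2, listed in section 3.1, and this is the only model in 15.1 that names week-24 performance.

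**Working it through.** **Inputs from the documents.**
- n=25 per cell is the plan's figure for its within-group analyses (section 15.2: "Within-group responder analyses conducted for completers"). n=75 is its number of completers per cohort, relevant because "these relationships will be tested separately for Cohort 1 and Cohort 2".
- r=.55 is the pilot correlation in section 2.2: those with the largest connectivity increases "also had the most general transfer on the MCCB in the experimental group". It is not a week-24 value. r=.34 is the smaller correlation named in section 15.2.
- Section 15.2 gives no number for week-24 power, so there is no plan figure to reproduce.

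**Assumed, because the documents give none.** ρ, the correlation of baseline with week-24 score, is .6 to .9 (with .5 as a milder case). c, the correlation of FC change with baseline score, is 0 to .3. q, the correlation of estimated IQ with baseline score, is .5 to .7. Tests are two-sided at .05.

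**Step 1: power when c=0.** Give baseline B and week-24 score Y unit variance. The gain Y−B has variance 2(1−ρ). If FC change F correlates r₀ with the gain and is independent of B:
- without B: r = r₀√(2(1−ρ))
- with B on step 1: partial r = r₀√(2/(1+ρ))
- power ≈ Φ(atanh(r)·√(n−3−k) − 1.96), where k=0 without B and 1 with B.

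Worked case, r₀=.55, ρ=.6, n=25. Without B: .55×√.8=.492, atanh .539, ×√22=2.53, power 71%. With B: .55×√1.25=.615, atanh .717, ×√21=3.28, power 91%.

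Power in percent, without / with the baseline score:

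| ρ | r₀=.55, n=25 | r₀=.55, n=75 | r₀=.34, n=25 | r₀=.34, n=75 |
|---|---|---|---|---|
| .5 | 83 / 93 | >99 / >99 | 38 / 48 | 85 / 94 |
| .6 | 71 / 91 | 99.5 / >99 | 31 / 45 | 76 / 92 |
| .9 | 22 / 83 | 57 / >99 | 11 / 39 | 26 / 87 |

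**Step 2: does baseline IQ stand in?** Section 8.3 describes it as a vocabulary-based screening estimate. With IQ as the only covariate, partial r = r₀√(2(1−ρ))/√(1−q²ρ²). For r₀=.55, n=25, q=.5 to .7: 74% to 79% at ρ=.6, and 25% to 32% at ρ=.9 (by simulation, 77% to 81% and 26% to 34%). It recovers part of the loss, and little when ρ is high.

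**Step 3: rejection when FC change has no effect beyond baseline.** Let Y = ρB + noise and corr(F,B)=c. Then corr(F,Y)=cρ. The same approximation, with both tails, gives these rejection rates over ρ=.6 to .9:

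| c | n=25 | n=75 |
|---|---|---|
| 0 | 5% | 5% |
| .1 | 6% to 7% | 8% to 12% |
| .2 | 9% to 14% | 18% to 34% |
| .3 | 14% to 26% | 34% to 65% |

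Simulations agree within error: 5% to 12% at c=.1, and 9% to 67% at c=.2 to .3 across both sample sizes. With B on step 1 the rate is 5%. With IQ only, simulated rates for c=.2 to .3 are 6% to 19% (n=25) and 9% to 51% (n=75). The rejection rate rises with n; the bias itself does not.

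**Step 4: errors of the alternatives.**
- Under the step 3 null, the change score correlates −c√((1−ρ)/2) with F. At c=.3, ρ=.6 this is −.134, rejected in 10% (n=25) or 21% (n=75).
- If instead the true score never changes and both scores have reliability R, the baseline-adjusted partial r is c√((1−R)/(1+R))/√(1−c²). At c=.3, R=.6 this is .157, rejected in 11% or 27%. The change score holds 5% here, and the level model rejects in 31% or 75%.

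**The case against.** The strongest reply is that the plan contains no stated error. Step 1 takes covariates from an open list, and a baseline score fits its description. That stands: a reader might infer that the plan excludes baseline adjustment, but the documents only fail to commit to it. All harm is conditional on leaving the score out.

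The regression is also supplementary. The main SA3 test uses improvements and is not affected, so a reader who concludes that SA3 as a whole confuses level with gain goes too far.

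It is tempting to add that step 2 leaves open whether FC level or FC change is entered. The sentence before it speaks of FC changes, so change is the natural reading; naming it is only tidiness.

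The figures depend on unsupported correlations. At c=0 there is no false-positive problem, and at ρ=.5 the level model has the same power as the change score (83% at r₀=.55, n=25). The sample sizes are illustrations too. Cohort 2 has two arms and is expected to be smaller than planned (sections 4.1 and 5.1), and remote participants may have no MRI (section 5.7) and hence no FC change.

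Finally, stability could mean holding the week-12 level. That is a fair reading, and it confirms that the reference must be stated. What does not fall away is that the model as described has no reference score and its stated aim needs one.

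**Conclusion.** The point holds as a specification gap worth closing. As written, the week-24 regression can be run in a form that answers a different question from its aim, and nothing elsewhere in the documents prevents that.

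The cost ranges from none to substantial. If FC change is unrelated to baseline, it is power only: at r=.55 and n=25, 71% to 22% against 91% to 83% for ρ from .6 to .9, and less at lower ρ. If they are related, an association with no retained gain is found in 5% to 12% of trials at c=.1 and 9% to 67% at c=.2 to .3, depending on n and ρ. These rates rest on assumed correlations.

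A reader might take the upper figures as the trial's expected false-positive rate; the documents do not support that. The week-24 association is itself real in those cases and misleads only if read as retained gain.

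Whether the N-back and DPX are collected at week 24 is a separate schedule clarification and no part of this conclusion.

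**What to change.** In the SA3 paragraph of section 15.1:

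1. For the week-24 regression, name the same measure's baseline score on step 1 with the other covariates, and FC change (week 12 minus baseline) on step 2.
2. Report the week-24-minus-baseline change score as a sensitivity analysis. State that baseline adjustment keeps some bias when baseline is measured with error, and that the change score keeps some under regression to the mean.
3. Say which reference stability refers to. If it is the week-12 level, report a week-12-adjusted model under its own label, as answering that question.

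The MCCB subtests are already scheduled at baseline in both cohorts, and the N-back and DPX belong to the baseline scan visit, so no new data are needed. The cost is SAP wording, one degree of freedom, and one extra sensitivity analysis that may disagree with the main one.
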